1.1 Synopsis

Protocol Title: Phase 4, Open-label Study to Evaluate Treatment Satisfaction With Erenumab in Patients With Migraine

Short Protocol Title: Erenumab Treatment Satisfaction Study

Study Phase: 4

Indication: Preventive treatment of migraine in adults

Rationale

Migraine is a prevalent and disabling neurological disorder, with a significant impact on the individual, family, workplace, and society. Objectives commonly assessed in registrational clinical trials **for migraine prevention** include changes in monthly migraine days and use of acute migraine-specific medications. These parameters, however, do not fully capture the whole breadth of the impact of migraine preventive treatments on the daily lives of patients and their families, including their satisfaction with treatment.

There is interest in the migraine provider community not only for clinical outcomes data, but also associated patient-centric data (eg, treatment satisfaction and global impression of change in migraine from different perspectives such as those of patients, providers and key family members). Health systems are also tracking patient satisfaction as a metric for quality of care delivery. These factors begin to define a new treatment paradigm for migraine management that includes both clinical and treatment-related satisfaction outcomes.

The Erenumab Treatment Satisfaction Study is a phase 4 United States (US), open-label, interventional, prospective 24-week study evaluating treatment satisfaction with erenumab as a preventive treatment in adult subjects with episodic migraine (EM) or chronic migraine (CM) currently on 1 standard of care migraine prevention therapy. The study will measure change in subject satisfaction with erenumab and subject, clinician, and key family member global impression of change in subject's migraine condition over the life of the study.

This study seeks to mirror real-world US clinical practice by providing subjects and investigators the flexibility to optimize erenumab dosing while maintaining or discontinuing the existing migraine prevention therapy (ie, standard of care).

Objective(s) and Endpoint(s)/Estimands

Objectives	Endpoints
Primary	

 To evaluate the effect of erenumab on medication-specific treatment satisfaction 	
 Change from baseline in the Treatment Satisfaction Questionnaire for Medication (TSQM) overall satisfaction scale score at week 24, as measured by items 12 to 14 of the TSQM version 1.4

Primary Estimand

The estimand for the primary efficacy objective consists of:

- The target population, which includes subjects with EM or CM currently on 1 standard of care migraine prevention therapy
- The endpoint, which is the change from baseline in TSQM overall satisfaction scale score at week 24, as measured by items 12 to 14 of the TSQM
- There are 2 intercurrent events, discontinuation of investigational product (IP) due to lack of efficacy or adverse event, and discontinuation of IP due to other reasons. The treatment effect of interest will be assessed for all subjects who receive least 1 dose of IP and have a baseline score and at least 1 post-baseline score on the TSQM overall satisfaction scale. A composite strategy will be used for subjects who discontinued IP due to lack of efficacy or adverse event with data after IP discontinuation, defined by the worst postbaseline value observed up to IP discontinuation (inclusive). A hypothetical strategy will be used for those subjects who discontinued IP due to other reasons with data collected after IP discontinuation censored.
- The treatment, which is erenumab 70 or 140 mg every 4 weeks
- The summary measure, which is the mean change from baseline in TSQM overall satisfaction scale score at week 24, as measured by items 12 to 14 of the TSQM

The primary estimand for the primary efficacy objective is the mean change from baseline in TSQM overall satisfaction scale score at week 24 in subjects with EM or CM who are currently on 1 standard of care migraine prevention therapy and who receive at least 1 dose of IP and have a baseline and at least 1 post-baseline TSQM overall satisfaction scale score, and a composite strategy will be used for subjects who discontinued IP due to lack of efficacy or adverse event with data after IP discontinuation defined by the worst postbaseline value observed up to IP discontinuation (inclusive), while a hypothetical strategy will be used for those subjects who discontinued IP due to other reasons with data collected after IP discontinuation censored.

Secondary


 • To assess the effect of erenumab on medication-specific treatment satisfaction 	
 • Achievement of overall satisfaction at week 24 as defined by subject reporting of satisfied, very satisfied, or extremely satisfied on Item 14 of the TSQM version 1.4
--	--

The estimand for the secondary efficacy objective on treatment satisfaction consists of:

- The target population, which includes subjects with EM or CM currently on 1 standard of care migraine prevention therapy
- The endpoint, which is achievement of overall satisfaction at week 24 as defined by subject reporting of satisfied, very satisfied, or extremely satisfied on Item 14 of the TSQM
- There are 2 intercurrent events, discontinuation of IP due to lack of efficacy or adverse event, and discontinuation of IP due to other reasons. The treatment effect of interest will be assessed for all subjects who receive at least 1 dose of IP and have a baseline value and at least 1 post-baseline value for Item 14 of the TSQM. A composite strategy will be used for subjects who discontinued IP due to lack of efficacy or adverse event where they will be defined as not satisfied after IP discontinuation. A hypothetical strategy will be used for those subjects who discontinued IP due to other reasons with data collected after IP discontinuation censored.
- The treatment, which is erenumab 70 or 140 mg every 4 weeks
- The summary measure, which is the proportion of subjects who achieves overall satisfaction at week 24

The estimand for the secondary efficacy objective on treatment-related satisfaction is the proportion of subjects who achieves overall satisfaction at week 24 as defined by subject reporting of satisfied, very satisfied, or extremely satisfied on Item 14 of the TSQM version 1.4, in subjects with EM or CM who are currently on 1 standard of care migraine prevention therapy and who receive at least 1 dose of IP and have a baseline value and at least 1 post-baseline value for Item 14 of the TSQM. A composite strategy will be used for subjects who discontinued IP due to lack of efficacy or adverse event where they will be defined as not satisfied after IP discontinuation, while a hypothetical strategy will be used for those subjects who discontinued IP due to other reasons with data collected after IP discontinuation censored.


 To assess the effect of erenumab on global impression of change in migraine (by subject, treating clinician, and key family member) 	
 Improvement in subject global impression at week 24, as defined by subject reporting of much improved or a little improved on the migraine Global Impression Item (mGI-I) Improvement in treating clinician's global impression at Week 24, as defined by treating clinician's reporting of much improved or a little improved on the mGI-I for each individual subject Improvement in key family member's impression at week 24, as defined by key family member's reporting of much improved or a little improved on the mGI-I for each individual subject
---	--

The estimand for the secondary efficacy objectives on impression of change in migraine consists of:

- The target population, which includes subjects with EM or CM currently on 1 standard of care migraine prevention therapy
- The endpoints, which include:
 - Improvement in subject global impression at week 24, as defined by subject reporting of much improved or a little improved on the mGI-I
 - Improvement in treating clinician's global impression at week 24, as defined by the clinician's reporting of much improved or a little improved on the mGI-I for each individual subject
 - Improvement in key family member's global impression at week 24, as defined by family member's reporting of much improved or a little improved on the mGI-I for each individual subject
- There are 2 intercurrent events, discontinuation of IP due to lack of efficacy or adverse event, and discontinuation of IP due to other reasons. The treatment effect of interest will be assessed for all subjects who receive at least 1 dose of IP and have at least 1 post-baseline value of each respective mGI-I item. A composite strategy will be used for subjects who discontinued IP due to lack of efficacy or adverse event where they will be defined as not improved after IP discontinuation. A hypothetical strategy will be used for those subjects who discontinued IP due to other reasons with data collected after IP discontinuation censored.
- The treatment, which is erenumab 70 or 140 mg every 4 weeks
- The summary measure, which is the proportion of subjects who achieves impression of improvement at week 24.

The estimand for the secondary efficacy objective on impression of change in migraine is the proportion of subjects who achieves global impression of migraine improvement at week 24 as defined by subject, treating clinician, or family member reporting of much improved or a little improved on the mGI-I, in subjects with EM or CM who are currently on 1 standard of care

migraine prevention therapy and who receive at least 1 dose of IP and have at least 1 post-baseline value of the respective MGI-I, and a composite strategy will be used for subjects who discontinued IP due to lack of efficacy or adverse event where they will be defined as not improved after IP discontinuation, while a hypothetical strategy will be used for those subjects who discontinued IP due to other reasons with data collected after IP discontinuation censored.

 To assess the effect of erenumab on subject functional impairment 	
 Change from baseline in physical function domain score at week 24, as measured by the Migraine Functional Impact Questionnaire (MFIQ) Change from baseline in usual activities domain score at week 24 as measured by MFIQ Change from baseline in emotional function domain score at week 24 as measured by MFIQ Change from baseline in social function domain score at week 24 as measured by MFIQ
---	--

The estimand for the secondary efficacy objective on subject functional impairment consists of:

- The target population, which includes subjects with EM or CM currently on 1 standard of care migraine prevention therapy
- The endpoints, which include:
 - Change from baseline in MFIQ physical function domain score at week 24
 - Change from baseline in MFIQ usual activities domain score at week 24
 - Change from baseline in MFIQ emotional function domain score at week 24
 - Change from baseline in MFIQ social function domain score at week 24
- There are 2 intercurrent events, discontinuation of IP due to lack of efficacy or adverse event, and discontinuation of IP due to other reasons. The treatment effect of interest will be assessed for all subjects who receive at least 1 dose of IP and have a baseline value and at least 1 post-baseline value of the respective MFIQ domain scores. A composite strategy will be used for subjects who discontinued IP due to lack of efficacy or adverse event with data after IP discontinuation defined by the worst postbaseline value observed up to IP discontinuation (inclusive). A hypothetical strategy will be used for those subjects who discontinued IP due to other reasons with data collected after IP discontinuation censored.
- The treatment, which is erenumab 70 or 140 mg every 4 weeks
- The summary measure, which is change from baseline in each MFIQ domain score at week 24

The estimand for the secondary efficacy objective on subject functional impairment is the change from baseline at week 24 in each MFIQ domain score, in subjects with EM or CM who are currently on 1 standard of care migraine prevention therapy and who receive at least 1 dose of IP and have a baseline value and at least 1 post-baseline value in each MFIQ domain score, and a composite strategy will be used for subjects who discontinued IP due to lack of efficacy or adverse event with data after IP discontinuation defined by the worst postbaseline value observed up to IP discontinuation (inclusive), while a hypothetical strategy will be used for those subjects who discontinued IP due to other reasons with data collected after IP discontinuation censored.

Overall Design

The study will comprise the following periods:

- A combined screening/baseline period consisting of the following:
 - A screening visit (which may coincide with the first day of the baseline period) for the assessment of eligibility criteria
 - A baseline period of approximately 4 weeks (no less than 28 days; up to 35 days) to collect data on migraine headaches and acute headache medication use using electronic diary (eDiary) and to assess compliance in eDiary usage
- A 24-week open-label treatment period

Subjects will sign the informed consent and be screened at the screening visit; eligible subjects may enter the baseline period at the same visit or may delay baseline procedures up to 3 weeks after the screening visit. At completion of the baseline period, those who meet eligibility criteria and choose to proceed will be enrolled and will enter the open-label treatment period.

The treating clinician and a key family member (if available) for each participating subject will be invited to complete an mGI-I at weeks 12, 16, 20, and 24/End of Study (EOS). The key family member must sign an informed consent before completing any study-specific procedures. The same clinician and key family member of each subject should complete the mGI-I across all visits. If the clinician or key family member is unable to complete a visit, the assessment for that visit should be noted as missed.

Qualitative interviews will be conducted with a selected subset of subjects, their treating clinicians, and key family members as part of an optional substudy. These interviews will be used to provide qualitative information on satisfaction/improvement and details into the drivers of satisfaction and improvement that might not be captured by self-assessment alone.

Number of Subjects

Approximately 322 subjects will be enrolled into the main study. The ratio of EM:CM will be approximately 1:1 to allow for qualitative assessments of satisfaction and impression of change in migraine for the two migraine types. A subset of approximately 20 enrolled subjects at select sites, their clinicians, and key family members will be invited to participate in an optional qualitative interview-based substudy with interviews to be conducted at the start and end of the study.

Summary of Eligibility Criteria

Subjects eligible for the study include those who are ≥ 18 years of age, have a history of migraine with or without aura for ≥ 12 months before screening, have ≥ 4 migraine days per month on average over the 3 months prior to screening, can be classified as EM or CM, report to their provider intolerance or insufficient response with their current preventive treatment, and demonstrate at least 75% compliance with the eDiary during the baseline period.

Key family members eligible for the study should be a family member/caregiver of an enrolled patient and a person in the subject's life with whom s/he interacts significantly on a day-to-day basis.

Clinicians eligible for the study must be licensed and practicing healthcare practitioners (HCPs) in the US and be currently treating the subject on Study 20190389.

For a full list of eligibility criteria, please refer to [Section 5.1](#) to [Section 5.2](#).

Treatments

Subjects will receive erenumab 70 or 140 mg once every 4 weeks (Q4W) by subcutaneous (SC) injections during the 24-week open-label treatment period. Erenumab will be packaged in a SureClick® Autoinjector (AI)/Pen(s) containing 1 mL of 70 mg/mL or 140 mg/mL of erenumab for SC injection.

All subjects will be started on a 70 mg dose of erenumab at day 1 with provider discretion for dose optimization, which is recommended to be completed by week 12. Dose optimization will allow subjects to remain on 70 mg, increase the dose from 70 to 140 mg, and if needed decrease the dose back down from 140 to 70 mg. After week 12, it is highly recommended that all subjects remain on the week 12 erenumab dose for the rest of the study. Additional dose adjustments after week 12 are not recommended and must only be made if deemed medically necessary by the investigator.

All subjects will be required to enter the study on 1 standard of care preventive medication for their migraine. Post-baseline, at their and the investigator's discretion, subjects will be allowed to remain on their standard of care preventive treatment, or they may fully discontinue standard of care therapy. Any changes to standard of care preventive treatment, including dose adjustments or tapering off medication, should be completed by the week 12 visit. Standard of care dose adjustments are not permitted after week 12.

Statistical Considerations

Sample Size Considerations:

The total sample size of approximately 322 subjects (effective sample size of 289 assuming 10% dropout at Week 24) is driven by the precision of the proportion estimates for the binary secondary endpoints, which target a half-width of around 5% for estimated 95% confidence intervals (CIs) (see [Table 9-1](#)).

Planned Analyses:

The final analysis will be conducted when all enrolled subjects have completed the week 24/EOS visit **and the data have been entered, cleaned, and locked**.

The primary endpoint will be analyzed using a repeated measures mixed effects model, including baseline TSQM overall satisfaction scale score, visit, the prevailing erenumab dose from week 12 onward, and baseline monthly migraine days (MMD) **based on observed data**. The least-squares mean (LSM) change from baseline in the TSQM overall satisfaction scale score at week 24 will be estimated, and the corresponding 95% CI will be provided.

Analysis of all secondary proportion endpoints will be descriptive only, where point estimates of the proportion and the corresponding 95% CI will be provided for each endpoint. All other secondary endpoints will be analyzed in a similar manner to the primary endpoint.

For a full description of statistical analysis methods, please refer to [Section 9](#).

[figure not shown]
Statistical Hypotheses

The study is descriptive in nature without a comparator arm, and as such no formal statistical hypothesis is defined.

Sponsor Name: Amgen Inc.

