All clinical outcomes assessments (COAs) detailed in the Schedule of Activities ([Table 1-1](#)) will be performed on the subject's eDiary device regardless of visit location.

The treating clinician and a key family member (if available) for each participating subject will be invited to complete an mGI-I at weeks 12, 16, 20, and 24/EOS. The key family member should be a person in the subject's life with whom s/he interacts significantly on a day-to-day basis. This person should have a deep understanding of the impact migraine has on the subject. They should also be able to provide their perspective of change in the subject's migraines over time. The person the subject chooses to nominate can be anyone such as a spouse, daughter or son, parent, sibling, or other relative or the person with whom the subject is in a de facto relationship. The key family member must sign an informed consent before completing any study-specific procedures. The same clinician and key family member of each subject should complete the mGI-I across all visits. If the clinician or key family member is unable to complete a visit, the assessment for that visit should be noted as missed.

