8.5.4 Summary of Substudy Participation Criteria

Study subjects must meet the following criteria to be considered for enrollment into the substudy:

- 1) Be enrolled in Study 20190389;
- 2) Have provided supplementary informed consent to participate in the substudy;
- 3) Be willing and able to participate in 2 telephone interviews lasting approximately 1 hour each;
- 4) Be able to read, understand, and speak English sufficiently to participate in the interviews;
- 5) Be willing to be audio-recorded during the interview sessions.

The key family member should be a family member/caregiver of an enrolled patient and should be the person in the subject's life that s/he interacts with the most on a day-to-day basis. Key family members must meet the following criteria to be considered for enrollment into the substudy:

- 1) Should have a deep understanding of the impact migraine has on the subject. They should also be able to provide their perspective of change in the subject's migraines over time. The person the subject chooses to nominate can be anyone such as a spouse, daughter or son, parent, sibling, or other relative or the person the subject is in a de facto relationship with.
- 2) Have provided informed consent to participate in the substudy;
- 3) Be willing and able to participate in 2 telephone interviews lasting approximately 1 hour each;
- 4) Be able to read, understand, and speak English sufficiently to participate in the interviews;
- 5) Be willing to be audio-recorded during the interview sessions.

Clinicians must meet the following criteria to be considered for enrollment into the substudy:

- 1) Be a US-licensed and practicing healthcare practitioner (HCP) at the clinical site (eg, neurologist, headache specialist, primary care physician, nurse practitioner, physician assistant) currently treating the subject on Study 20190389;

- 2) Be willing and able to participate in 2 telephone interviews lasting approximately 1 hour each;
- 3) Be able to read, understand, and speak English sufficiently to participate in the interviews;
- 4) Be willing to be audio-recorded during the interview sessions.

Meeting any of the following criteria will exclude a subject, key family member, or clinician from enrollment into the substudy:

- 1) Expected to be unable to complete entry interview within 7 days from first investigational product dose;

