Site staff will identify potential subjects from their existing patient population or may seek referral patients through existing professional networks or other community sources such as patient advocacy groups. All patient facing materials must be reviewed/approved by the sponsor (Amgen Inc.) and the local IRB/IEC.

Informed Consent Process

An initial sample informed consent form is provided for the investigator to prepare the informed consent document to be used at his or her site. Updates to the sample informed consent form are to be communicated formally in writing from the Amgen Trial Manager to the investigator. The written informed consent form is to be prepared in the language(s) of the potential participant population.

The investigator or his/her delegated representative will explain to the participant (ie, study subject or key family member) the aims, methods, anticipated benefits, and potential hazards of the study and optional sub-study before any protocol-specific screening procedures or any investigational product(s) is/are administered, and answer all questions regarding the study and substudy.

Participants must be informed that their participation is voluntary. Participants will then be required to sign a statement of informed consent that meets the requirements of 21 CFR 50, local regulations, ICH guidelines, Health Insurance Portability and Accountability Act requirements, where applicable, and the IRB/IEC or study site.

The subject's medical record must include a statement that written informed consent was obtained before the subject was enrolled in the study and the date the written consent was obtained. The authorized person obtaining the informed consent must also sign the informed consent form.

The investigator is also responsible for asking the subject if the subject has a primary care physician and if the subject agrees to have his/her primary care physician informed of the subject's participation in the clinical study unless it is a local requirement. The investigator shall then inform the primary care physician. If the subject agrees to such notification, the investigator is to inform the subject's primary care physician of the subject's participation in the clinical study. If the subject does not have a primary care physician and the investigator will be acting in that capacity, the investigator is to document such in the subject's medical record.

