When a large, multicenter group has conducted the work, the group is to identify the individuals who accept direct responsibility for the manuscript. These individuals must fully meet the criteria for authorship defined above. Acquisition of funding, collection of data, or general supervision of the research group, alone, does not justify authorship. All persons designated as authors must qualify for authorship, and all those who qualify are to be listed. Each author must have participated sufficiently in the work to take public responsibility for appropriate portions of the content. All publications (eg, manuscripts, abstracts, oral/slide presentations, book chapters) based on this study must be

submitted to Amgen for review. The Clinical Trial Agreement among the institution, investigator, and Amgen will detail the procedures for, and timing of, Amgen's review of publications.

Investigator Signatory Obligations

Each clinical study report is to be signed by the investigator or, in the case of multicenter studies, the coordinating investigator.

The coordinating investigator, identified by Amgen, will be any or all of the following:

- A recognized expert in the therapeutic area
- An Investigator who provided significant contributions to either the design or interpretation of the study
- An Investigator contributing a high number of eligible subjects

Data Quality Assurance

All subject data relating to the study will be recorded on printed or electronic CRF (eCRF) unless transmitted to the sponsor or designee electronically (eg, laboratory data, centrally or adjudicated data). The investigator is responsible for verifying that data entries are accurate and correct by physically or electronically signing the eCRF.

The investigator must maintain accurate documentation (source data) that supports the information entered in the eCRF.

The investigator must permit study-related monitoring, audits, IRB/IEC review, and regulatory agency inspections and provide direct access to source data documents.

The sponsor or designee is responsible for the data management of this study including quality checking of the data.

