Achievement of overall satisfaction at week 24 as defined by subject reporting of satisfied, very satisfied, or extremely satisfied on Item 14 of the TSQM version 1.4	
1. Summary statistics using observed data (after intercurrent event handling);
 
2. The achievement of overall satisfaction at week 24 as defined by subject reporting of satisfied, very satisfied, or extremely satisfied on Item 14 of the TSQM version 1.4 will be analyzed using a generalized linear mixed effects model with the logit link function. The model will include baseline achievement of overall satisfaction, visit, the prevailing erenumab dose from Week 12 onwards, and baseline MMD based on observed data. The proportions and the corresponding 95% CI at week 24 will be estimated from the LSM (with inverse link function) of the mixed effects model.
 
3. The efficacy analysis set will be used for this endpoint analysis.

Improvement in subject global impression at week 24 , as defined by subject reporting of much improved or a little improved on the mGI-I	
1. Summary statistics using observed data (after intercurrent event handling);
 
2. The Improvement in global impression at week 24, as defined by subject's, clinician's, and key family member's reporting of much improved or a little

Endpoint	Primary Summary and Analysis Method

defined by treating clinician's reporting of much improved or a little improved on the mGI-I
 
Improvement in key family member's global impression at week 24, as defined by key family member's reporting of much improved or a little improved on the mGI-I
	
improved on the migraine Global Impression Item (mGI-I) will be analyzed separately using a generalized linear mixed effects model with the logit link function. The model will include the visit, the prevailing erenumab dose from Week 12 onwards, and baseline MMD based on observed data. The proportions and the corresponding 95% CI at week 24 will be estimated from the LSM (with inverse link function) of the mixed effects model.
 
3. The efficacy analysis set will be used for this endpoint analysis.

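### The clinician mGI-I analysis makes no allowance for several subjects sharing a rater; if they do and ratings correlate within clinician, its 95% CI will be too narrow

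*Protocol*

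**What the plan says.** Protocol 1.1 and Section 3 define three mGI-I secondary endpoints, one each for the subject, the treating clinician and a key family member. The clinician endpoint is met when the treating clinician reports "much improved or a little improved on the mGI-I for each individual subject". The estimand's summary measure is the proportion of subjects with an impression of improvement at week 24.

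On who rates, Protocol 4.1 says: "The same clinician and key family member of each subject should complete the mGI-I across all visits". This fixes the rater within a subject over time. It says nothing on how many subjects one clinician rates.

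On the analysis, SAP Table 9-2 says that the three perspectives "will be analyzed separately using a generalized linear mixed effects model with the logit link function", and of the terms: "The model will include the visit, the prevailing erenumab dose from Week 12 onwards, and baseline MMD based on observed data". Protocol 9.4.2.2, SAP 4.1 and SAP 9.5.2 list the same terms. None of them names a clinician or site term, a cluster-robust variance or a sensitivity analysis for clustering. The only sensitivity analysis in SAP 9.1 concerns intercurrent events for the primary endpoint. The possible sources of bias in SAP 8.4 do not include raters or sites. The model is called mixed, but no random effect or covariance structure is written down, not even for subject.

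On precision, Protocol 9.2 bases the sample size on the CI half-width for the binary secondary endpoints, with a target of around 5%. SAP Table 3-2 restates the half-widths for 240 enrolled and 216 effective subjects after the early stop to enrolment.

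**The concern.** One model serves all three perspectives, although their raters differ in kind. A subject rates only himself or herself, and a family member normally rates one subject. A treating clinician may rate many.

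Several passages make shared clinician raters likely. Protocol Appendix 3 says: "Site staff will identify potential subjects from their existing patient population". The same appendix describes a possible coordinating investigator as "An Investigator contributing a high number of eligible subjects". The substudy criteria in Protocol 8.5.4 require the clinician to "Be a US-licensed and practicing healthcare practitioner (HCP) at the clinical site". With 240 subjects recruited this way, a separate clinician for each is hard to believe.

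The rating is a single subjective item given open-label, and a report of slight improvement counts as success. Clinicians may well differ in how readily they give it, in which case outcomes of subjects who share a clinician are correlated. There is no comparator arm in which a rater effect could cancel, so between-clinician variance enters the error of the one proportion. The study tests no hypothesis, so the estimate and its interval are the whole result for this endpoint. An interval that is too short would overstate what is known from the clinician's perspective.

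**Working it through.** **Inputs from the documents.** Effective n = 216 (SAP 3.2: 240 × 0.9 = 216). Stated half-widths from SAP Table 3-2: 6.7%, 6.5%, 6.1% and 5.3% at 50%, 60%, 70% and 80%.

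**Inputs assumed.** Subjects per clinician, m, and the intra-clinician correlation, ICC. Neither document gives them. The values below are illustrations, with clusters of equal size.

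**Step 1: reproduce the plan's figures.** The simple binomial half-width is 1.96 × √(p(1−p)/n).
- n = 216: 6.67%, 6.53%, 6.11%, 5.33%. These agree with Table 3-2.
- n = 289: 5.76%, 5.65% (5.648 before rounding), 5.28%, 4.61%. These agree with Protocol Table 9-1.

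Both tables are therefore independent-subject binomial figures with no allowance for clustering.

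**Step 2: design effect.** DE = 1 + (m − 1) × ICC. The clustered half-width is 6.11% × √DE at p = 70%. The coverage of an interval that ignores clustering is 2Φ(1.96/√DE) − 1.

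| m | ICC | DE | Half-width at 70% | Coverage of uncorrected interval |
|---|---|---|---|---|
| 1 | any | 1.00 | 6.1% | 95.0% |
| 2 | 0.05 | 1.05 | 6.3% | 94.4% |
| 2 | 0.20 | 1.20 | 6.7% | 92.6% |
| 4 | 0.05 | 1.15 | 6.6% | 93.2% |
| 4 | 0.10 | 1.30 | 7.0% | 91.4% |
| 4 | 0.20 | 1.60 | 7.7% | 87.9% |
| 8 | 0.05 | 1.35 | 7.1% | 90.8% |
| 8 | 0.10 | 1.70 | 8.0% | 86.7% |
| 8 | 0.20 | 2.40 | 9.5% | 79.4% |

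Worked example for m = 8 and ICC = 0.20: DE = 1 + 7 × 0.20 = 2.40; √2.40 = 1.549; 6.11% × 1.549 = 9.5%; 1.96/1.549 = 1.265, which gives 79.4%.

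**Step 3: simulation check.** 216 subjects were simulated with normal clinician and subject effects on the logit scale (subject SD 1.0) and about 68% to 70% improved. A simple binomial interval was compared with a clinician-clustered robust interval, using a t quantile on the number of clinicians minus 1.

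| Clinicians × subjects | Clinician SD | Binomial coverage | Clustered coverage |
|---|---|---|---|
| 36 × 6 | 0 | 94.0% | 94.8% |
| 108 × 2 | 0.8 | 93.1% | 95.2% |
| 36 × 6 | 0.8 | 89.6% | 95.6% |
| 27 × 8 | 0.8 | 86.7% | 94.4% |

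The direction agrees with Step 2, and the clustered interval holds close to 95% whether or not clinicians differ. The planned mixed model itself was not fitted, so these figures show the scale of the effect on a simple proportion and not the error of the interval that will be reported.

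**The case against.** The strongest reply is that the documents do not establish the clustering. A reader might infer that one clinician certainly rates several subjects and that the interval will certainly be too narrow. The text does not support that. No number of sites, clinicians or subjects per clinician is given, and no ICC. The rule in Protocol 4.1 is about one subject's visits. The wording that places the clinician at the site is a substudy criterion; for the main study, Protocol 1.1 asks only for a licensed US practitioner who is treating the subject in the study. This stands, and the point has to be conditional.

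Five further replies have weight.
- **The random part is unspecified.** The listed terms read as fixed effects, and no random effect is stated. The plan is silent on clustering; it does not declare subjects independent. That is correct, but silence leaves no commitment to handle it.
- **The composite rule dilutes rater leniency.** Subjects who stop treatment for lack of efficacy or an adverse event count as not improved afterwards, whatever the clinician would say. This may lower the ICC by an unknown amount.
- **The illustration depends on its range.** The 79% figure needs 8 subjects per clinician and ICC 0.20 together. At the low end the effect disappears.
- **Clinicians could be treated as fixed.** Between-clinician variance then need not enter the interval. The documents do not say which view they take.
- **The stakes are modest.** No formal test depends on this interval, and the sponsor already accepted a half-width of 6.7% in place of 5.8% at 50% when it stopped enrolment at 240.

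These replies limit the size and weight of the point. None supplies a method that deals with shared raters.

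**Conclusion.** The point holds in conditional form. The plan has no provision for correlation between subjects rated by the same clinician. If clinicians rate several subjects and ratings correlate positively within clinician, the 95% CI for the week 24 clinician proportion will be too narrow. The first condition is very likely given site-based recruitment. The second is plausible for an open-label, subjective rating. Neither is documented.

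The size is not known. For the assumed range of 4 to 8 subjects per clinician and ICC 0.05 to 0.20, the half-width at 70% and n = 216 grows from 6.1% to between 6.6% and 9.5%, and true coverage lies between 93% and 79%.

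The point is confined to the clinician mGI-I. The primary endpoint and the subject and family mGI-I endpoints are outside it. It is a cheap improvement to one secondary interval and does not call the study's main result into question.

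**What to change.** For the clinician mGI-I only, report the week 24 proportion with a 95% CI from a marginal method clustered on rating clinician, for example GEE or cluster-robust standard errors. Keep the intercurrent-event rules as they are. Cluster on site if no rater identifier is held. If clusters are few, base the interval on a t quantile with the number of clusters minus 1, as in the simulation above. Report the number of raters and the distribution of subjects per rater beside the estimate. The result can stand next to the planned model as a sensitivity analysis.

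Do not rely on a clinician random intercept in the logit model with a back-transformed LSM. That describes a typical clinician, whereas the estimand names the proportion of subjects, so it would change the target as well as the width.

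The cost is a little extra analysis and possibly a wider interval. The documents do not mention a stored rater identifier, so clinician-level clustering may need one to be retrieved; site-level clustering should need no new data. If the ICC is near zero, the interval will hardly change.
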